1. ACTH will be initiated 2 weeks prior to the completion of the prednisone taper for patients who are receiving prednisone at the time of consent.
2. ACTH will be initiated 2 weeks prior to stopping preventive medications such as tacrolimus, cyclosporin, and mycophenolate.

Patients randomized to no treatment will be followed for up to 6 months or until disease relapse, whichever occurs first. Patients who relapse within 6 months will be given the option of reassignment to the ACTH treatment group after remission has been achieved using conventional corticosteroid therapy.

Patients randomized to ACTH treatment will be given ACTH for 12 months. During the second 6 months, the ACTH dose will be reduced to 50% of the starting dose. The outcome of interest is the presence of relapses after dose reduction. Follow-up will occur throughout the 12 months of therapy, and also for 6 months following the completion of ACTH therapy. The outcome of interest is the percentage of patients with relapses in the 6 months after completing a 12 month course of ACTH treatment.

Visits

Screening visit: The study will be explained to the patient and family. Inclusion and exclusion criteria will be reviewed to determine eligibility. Consent and assent will be obtained as appropriate. Medical history will be recorded. A physical exam will be performed. If indicated, a

plan for prednisone tapering will be explained to the family. The date of the baseline visit will either be determined at that visit or via telephone for patients who are currently in relapse.

Baseline visit: The patient will be seen and have baseline labs (renal function panel, cholesterol, urinalysis, urine protein/creatinine ratio). A urine pregnancy test will be performed in females of childbearing age (achieved menarche) who are randomized to ACTH treatment along with counseling in required birth control. An interval medical history and quality of life (QOL) survey will be performed. Patients will have a physical examination. Patients will be randomized to either ACTH gel or no treatment. Patients will be given Albutix and instructions for daily monitoring of the urine and recording the results. Patients randomized to ACTH gel will receive their first injection in clinic and be taught how to perform injections at home. A stop date for other immunosuppressive medications will be provided, if appropriate, 2 weeks after starting ACTH.

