Patients who are randomized to no treatment will have follow-up visits up to the time of relapse, at 1 month, 2 months, 4 months, and 6 months. An interval medical history (including screening for adverse events) will be performed. Patients will have a physical examination. A renal function panel, cholesterol, urinalysis, and urine protein/creatinine ratio, and QOL survey will be obtained at month 6. They will be treated with prednisone for any relapses and have the option to be placed on ACTH during the last 2 weeks of the prednisone taper if the relapse occurred within 6 months of the baseline visit. The subsequent visit schedule and procedures will be identical to the schedule for subjects initially randomized to ACTH (i.e., it will include a baseline visit, telephone contacts, and 18 months of follow-up). Alternatively, the patient may elect to be treated via standard of care in collaboration with the treating nephrologist, and the patient will then exit the study.

Flow Chart of Study Course

Participant Selection

Sixty subjects will be recruited from 10-12 large pediatric centers. Subjects may also be identified via physician or self-referral from advertisements placed on NephCure. Additionally, subjects may be recruited from registries of individuals interested in research participation.

Patients and their caregivers will be approached during a relapse of nephrotic syndrome or within 4 months of a relapse. The following criteria will be reviewed during the screening visit to determine eligibility:

Inclusion criteria

1. Age >1 year at onset of nephrotic syndrome
2. Age 2-20 years at time of randomization
3. Estimated GFR > 50 ml/min/1.73 m² at most recent measure prior to randomization (Schwartz formula)
4. Steroid responsive nephrotic syndrome throughout clinical course (never required a second agent to attain remission of a relapse of nephrotic syndrome)
5. History of frequently relapsing or steroid dependent nephrotic syndrome (defined as 2 or more relapses within 6 months after initial therapy or 4 or more relapses in any 12 month period OR relapse during taper or within 2 weeks of discontinuing prednisone).
6. Patient is currently in relapse of nephrotic syndrome or had a relapse within the last 4 months (defined as an increase in the first morning urine protein to creatinine ratio ≥ 2 or Albustix reading of ≥ 2 for 3 or 5 consecutive days).

Exclusion criteria

1. Prior treatment with ACTH.

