Treatment assignments will be stratified according to clinical center. The treatment assignments will be generated by the Data Coordinating Center (DCC) with the use of a pseudo-random-number generator with randomly permuted blocks that will be used to ensure balance between the number of subjects assigned to each treatment (ACTH or no ACTH). Before the study starts, the institutional research coordinator at each clinical center will be given a batch of

20 sealed, sequenced, opaque envelopes containing the treatment assignment and will have a unique ID consisting of the clinical center stratum.

Patients will be assigned to one of the two treatment arms in a ratio of 1:1.

Data Collection and Management

Data confidentiality

Information about study subjects will be kept confidential and managed under the applicable laws and regulations. Those regulations require a signed subject authorization informing the subject of the following:

- What protected health information (PHI) will be collected from subjects in this study
- Who will have access to that information and why
- Who will use or disclose that information
- The rights of a research subject to revoke their authorization for use of their PHI.

In the event that a subject revokes authorization, the Investigator, by regulation, retains the ability to use all information collected prior to the revocation of subject authorization. For subjects that have revoked authorization, attempts should be made to obtain permission to collect follow-up safety information (e.g. has the subject experienced any new or worsened AEs) at the end of their scheduled study period.

Data collection

Data collection and analysis will be facilitated by the Data Coordination Center (DCC), which will be led by [name]. They will interact with the PIs, local site investigators, and study coordinators to collect data, analyze the results, and provide reports to the DSMB in a timely manner.

REDCap will be used for data collection and management. The data collection system for this study uses built-in security features to encrypt all data for transmission in both directions, preventing unauthorized access to confidential participant information. Access to the system will be controlled by a sequence of individually assigned user identification codes and passwords, made available only to authorized personnel who have completed prerequisite training.

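### Site-held envelopes from centre-stratified permuted blocks leave the next arm guessable if blocks are small, and the plan describes no outside control over their opening

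*Combined protocol and SAP*

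**What the plan says.** Treatment Assignment and Randomization sets out the method:

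- "Treatment assignments will be stratified according to clinical center".
- The Data Coordinating Center (DCC) generates the list with a "pseudo-random-number generator with randomly permuted blocks that will be used to ensure balance between the number of subjects assigned to each treatment".
- On custody, "the institutional research coordinator at each clinical center will be given a batch of" assignments, and this is done ahead of the trial's start. Each batch consists of "20 sealed, sequenced, opaque envelopes containing the treatment assignment".
- "Patients will be assigned to one of the two treatment arms in a ratio of 1:1".

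Participant Selection gives the scale: "Sixty subjects will be recruited from 10-12 large pediatric centers". Study Design and Methods describes the trial as open label.

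Under Visits, consent is taken at screening and randomization takes place at a separate baseline visit. On timing: "The date of the baseline visit will either be determined at that visit or via telephone for patients who are currently in relapse".

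The document gives no block size. It does not say whether the size varies or is withheld from sites. It describes no rule for when an envelope may be opened, and no log or audit of opening.

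**The concern.** Sealed opaque envelopes, properly handled, stop a site reading ahead. They do not stop it reasoning from assignments it already knows. In an open-label trial with a separate block sequence at each centre, whoever tracks the local count knows which arm is behind. If a block is nearly used up and its size is known, the next arm may be certain.

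A site could act on this by bringing one child to baseline before another, by delaying a visit, or by choosing when to approach a family within the 4-month window after a relapse. The envelopes are in local custody, and the document describes no outside check on the order or time of opening.

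What is at stake is the primary comparison of 6-month relapse. If children at higher or lower risk are steered to one arm, the difference is biased. Analysis by randomized arm does not remove that bias, and adjustment cannot reliably correct selection on unmeasured prognosis.

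**Working it through.** **Inputs.** From the documents: 60 children; 10–12 centres, so 60/12 = 5 to 60/10 = 6 per centre; 1:1 allocation in permuted blocks within centre; boundary p-values of 0.006 at 30 patients and 0.045 at 60. Assumed, because not stated: block sizes of 2, 4, 6, 10 and 20. All but 6 divide a batch of 20 evenly.

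**The plan's own figure.** The plan gives none for predictability. Its nearest figure is 91% power for 70% versus 30% relapse with 30 per arm. SE = √(0.7×0.3/30 + 0.3×0.7/30) = 0.118, and 0.40/0.118 = 3.38. Subtracting the two-sided 0.045 critical value of 2.00 leaves 1.38, which gives 91.6% (91.7% with both looks). Exact-binomial simulation of both looks gives about 90%. The stated 91% is reproduced within 2 points, and this point does not change it. The two boundaries imply an overall two-sided error of 4.75%.

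**Guessing by hand, block of 4.** The rule is to name the arm that is behind. The chance of being right is 1/2 for child 1 and 2/3 for child 2. For child 3 it is (1/3)×1 + (2/3)×(1/2) = 2/3, and for child 4 it is 1.

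- Five children: (1/2 + 2/3 + 2/3 + 1 + 1/2)/5 = 67% correct. Certain: (1/3 + 1)/5 = 27%.
- Six children: 4/6 = 67% correct. Certain: (1/3 + 1)/6 = 22%.

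The guess needs only the running count at the centre. Certainty also requires knowing or working out the block size.

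**Whole trial.** This is a simulation of 60 children over 11 equal-chance centres. No true effect and a mean relapse risk of 50% are assumed. Each child's risk is shifted 10 points down when ACTH is predicted and 10 points up when no treatment is predicted. The test is a pooled z test at both looks.

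If g is the share of correct guesses, with ties counted as one half, the false difference when every guess is acted on is 2 × 0.10 × (2g − 1). For example, block 2 gives 0.20 × (2×0.73 − 1) = 0.092.

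| Block size | Next arm certain | Best guess correct | False difference, every guess used | Type I error, every guess used |
|---|---|---|---|---|
| 2 | 45% | 73% | 9 points | about 11% |
| 4 | 26% | 67% | 7 points | about 9% |
| 6 | 15% | 64% | 6 points | about 7–8% |
| 10 | 2% | 58% | 3 points | about 6% |
| 20 | 0% | 53% | 1 point | about 5–6% |

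With no steering, the same simulation rejects in about 5–6% of runs.

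**Partial steering.** If sites act on half their guesses, the false difference halves, to about 4.6 / 3.4 / 2.8 points at blocks of 2 / 4 / 6, and type I error is about 5–7%. If they act on a quarter, the false difference is about 2 points and type I error about 6%.

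**Varying blocks alone.** Mixing sizes 4 and 6 within centre leaves about 65% correct guesses, against 67% for a fixed block of 4.

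**The case against.** Much can be said on the other side.

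- **Block size.** A reader might infer that sites can often predict the next arm. The documents do not support that outright. Blocks of 10 or 20 also fit a batch of 20, and with them the harm nearly vanishes. The stated aim of balance makes small blocks more plausible at 5–6 children per centre, but that is an inference.
- **Freedom over dates.** A reader might infer that the site simply picks the date. For children in relapse, randomization waits for remission. For those on prednisone, ACTH starts 2 weeks before the taper ends, and the first injection is given at the baseline visit. Some discretion remains, but it is bounded.
- **Opportunity.** Swapping two children needs both ready at one small centre. That may be uncommon, although delaying a visit or choosing when to approach a family needs only one child. Acting on every guess is therefore an upper case.
- **Motive.** Children in the no-treatment arm who relapse within 6 months may receive ACTH afterwards. This weakens the incentive to steer without removing it.
- **Larger shifts.** A 20-point shift either way would give type I error of about 29% / 20% / 13% at blocks of 2 / 4 / 6. It implies a 40-point risk gap between steered children, for which the documents give no basis.
- **Existing controls.** A reader might infer that allocation is not concealed at all. Envelopes are sealed, opaque, sequenced and carry an ID; the DCC reviews entered data; and site monitoring sits in a separate plan not available here. The supportable statement is that this document describes no outside control over opening.

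These points limit the size of the concern. They do not answer the central one: past assignments are known locally, and nothing described here ties each opening to a child already committed.

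**Conclusion.** The concern holds in a limited form. Local custody of the whole sequence, centre strata, open treatment and about 5–6 children per centre make the next arm guessable if blocks are small, and the plan neither rules out small blocks nor describes a check on opening.

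The resulting bias is possible, not shown. With a 10-point shift either way, no true effect and 50% mean risk, type I error is about 5–7% when half the guesses are used at blocks of 2–6. It is at most about 8–11% when all are used, and close to nominal at blocks of 10 or more. The shift and the share of guesses acted on are assumptions; the documents fix neither. Sample size and stated power are unaffected. The case for change rests on the low cost of a better method and on the difficulty of repairing selection bias afterwards.

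**What to change.** In Treatment Assignment and Randomization, replace site-held envelopes with release by the DCC through REDCap, which the trial already uses. Each assignment should be released for one child at a time, time-stamped and irrevocable. Release should come only after consent, confirmed eligibility and baseline assessments are entered and locked.

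The baseline visit text needs reconciling with that lock. Pregnancy is an exclusion criterion, yet the baseline test is described only for those randomized to ACTH, so one eligibility check can follow knowledge of the arm.

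State that block sizes vary and are not disclosed to sites. Also state the limit of this step: non-disclosure removes most certainty, but blocks of 4 and 6 within centre still leave about 65% correct guesses, because naming the arm that is behind needs no block size. The protection comes mainly from locked central release. Even that does not stop a site choosing when to present a child, but it removes local custody and leaves an auditable order.

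The cost is a REDCap form and DCC set-up before the first child is randomized, a short wait at the baseline visit, and slightly looser balance within centre. No extra patients are needed.
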